## 1. Abbreviations

ASaT	All Subjects as Treated
BMI	Body Mass Index
DMC	Data Monitoring Committee
FAS	Full Analysis Set
GMT	Geometric Mean Titer
GMI	Geometric Mean Increase
HIV	Human Immunodeficiency Virus
ITT	Intent to Treat
LOCF	Last Observation Carried Forward
MedDRA	Medical Dictionary for Regulatory Activities
PPS	Per Protocol Set
PT	Preferred Term
SAE	Serious Adverse event
SD	Standard Deviation
SOC	System Organ Class
SS	Safety Set
TEAE	Treatment Emergent Adverse Event

## 2. Purpose

To evaluate the safety and immunogenicity of inactivated SARS-CoV-2 Vaccine (Vero cell) in adults.

### 2.1 Clinical Trial Phase I

To evaluate the safety, tolerance, and preliminary immunogenicity of different dosage vaccine administered at different immunization schedules in adults.

### 2.2 Clinical Trial Phase II

To evaluate the safety and preliminary immunogenicity of different dosage vaccine administered at different immunization schedules in adults to determine the appropriate dosage and immunization schedule for further clinical evaluation.

## 3. Design

### 3.1 Overall Design

Single centered, randomized, double-blinded, and placebo-controlled clinical trial design is adopted.

A total of 144 healthy adults aged 18~59 years old are selected as subjects in phase I. After informed consent, subjects who pass the physical examination, meet the inclusion criteria and did not meet the exclusion criteria will be enrolled into the study. The subjects for the emergency immunization schedule (day 0, 14) and routine immunization schedule (day 0, 28) respectively, with 72 subjects for each immunization schedule. Simultaneously, subjects are phased enrolled, with 36 at medium dosage stage which will run-in first, following by 36 at high dosage stage. The subjects enrolled in each dosage stage will be randomly assigned in a 2:1 ratio to receive vaccine or placebo. The high dosage stage vaccination will start only with the condition that safety observation 0~7 days after the first dose of the medium dosage stage vaccination is finished, and the good safety profiles are confirmed by the DMC, according to the occurrence of the solicited and unsolicited adverse events, as well as the occurrence of the abnormal results of the blood routine, blood biochemistry, and urine routine testing.

The phase II clinical trial will start only with the condition that safety observation 0~7 days after the first dose of the high dosage stage vaccination is finished, and the good safety profiles are confirmed by the DMC. A total of 600 healthy adults aged 18~59 years old are selected as subjects. After informed consent, subjects who pass the physical examination, meet the inclusion criteria and didn't meet the exclusion criteria will be enrolled into the study. Subjects will receive two doses of injection at the emergency immunization schedule of day 0,14 or routine immunization schedule of day 0,28, with 300 subjects for each immunization schedule. The subjects for each schedule will be

randomly assigned in a 2:2:1 ratio to receive the medium dosage, high dosage vaccine, or placebo.

Safety Observation: The immediate reactions occur within 30 minutes after each dose of vaccination will be observed on site. The local and systemic solicited adverse events (AEs) occur within 0~7 days after each dose vaccination, as well as the unsolicited AEs from the beginning of the vaccination to 28 days after the whole schedule vaccination will be collected. Additionally, the SAEs from the beginning of the vaccination until 6 months after the whole schedule vaccination will be collected. Besides, venous blood and urine sample will be collected from all subjects in phase I at different time points before and after vaccination for the blood routine, blood chemistry, urine routine testing, and the testing of serum inflammatory factor and antinuclear antibody, to evaluate the safety; venous blood will be collected from all subjects in phase II at different time points before and after vaccination for the antinuclear antibody. In the safety observation, blood and urine collection at each time point are shown in Table 1.

**Table 1 Blood and urine collection at each time point in safety observation**

Phase and immunization schedule	Sample type	Test contents	Sampling time
Phase I - emergency immunization schedule	Blood	Blood Routine, Blood Chemistry	Before the first dose of inoculation (D-7~D0), 3 days after the first dose of inoculation (D3), before the second dose inoculation (D14), 3 days after the second dose of inoculation (D17)
		Inflammatory Factor	Before the first dose of inoculation (D0), 7 days after the first dose of inoculation (D7), before the second dose inoculation (D14), 7 days after the second dose of inoculation (D21)
		Antinuclear Antibody	Before the first dose of inoculation (D0), 7 days after the first dose of inoculation (D7), 14 days after the first dose of inoculation (D14), 21 days after the first dose of inoculation (D21), 28 days after the first dose of inoculation (D28), 42 days after the first dose of inoculation (D42), 6 months after the whole schedule vaccination (D194)
Phase I - routine immunization schedule	Urine	Urine Routine	Before the first dose of inoculation (D-7~D0), 3 days after the first dose of inoculation (D3), before the second dose inoculation (D14), 3 days after the second dose of inoculation (D17)
	Blood	Blood Routine, Blood Chemistry	Before the first dose of inoculation (D-7~D0), 3 days after the first dose of inoculation (D3), before the second dose inoculation (D28), 3 days after the second dose of inoculation (D31)
		Inflammatory Factor	Before the first dose of inoculation (D0), 7 days after the first dose of inoculation (D7), before the second dose inoculation (D28), 7 days after the second dose of inoculation (D35)
		Antinuclear Antibody	Before the first dose of inoculation (D0), 28 days after the first dose of inoculation (D28), 35 days after the first dose of inoculation (D35), 42 days after the first dose of inoculation (D42), 56 days after the first dose of inoculation (D56), 6 months after the whole schedule vaccination (D208)
Urine	Urine Routine	Before the first dose of inoculation (D-7~D0), 3 days after the first dose of inoculation (D3), before the second dose inoculation (D28), 3 days after the second dose of inoculation (D31)	
Phase II - emergency immunization schedule	Blood	Antinuclear Antibody	Before the first dose of inoculation (D0), 28 days after the first dose of inoculation (D28), 42 days after the first dose of inoculation (D42), 6 months after the whole schedule vaccination (D194)
Phase II - routine immunization schedule	Blood	Antinuclear Antibody	Before the first dose of inoculation (D0), 28 days after the whole schedule vaccination (D56), 6 months after the whole schedule vaccination (D208)

Immunogenicity observation: blood samples were collected from all subjects at different time points before and after immunization for the detection of serum neutralizing antibodies. In phase I, IgG, IgM antibodies, and specific T cell response assay (IFN- $\gamma$  detection using Elispot method) were also required. In the immunogenicity observation, the blood collection at each time point is shown in Table 2.

**Table 2 Blood collection at different time points in immunogenicity observation**

Phase and immunization schedule	Test contents	Sampling time
Phase I - emergency immunization schedule	Neutralizing antibody, IgG, IgM	Before the first dose of inoculation (D0), 7 days after the first dose of inoculation (D7), 14 days after the first dose of inoculation (D14), 21 days after the first dose of inoculation (D21), 28 days after the first dose of inoculation (D28), 42 days after the first dose of inoculation (D42), 6 months after the whole schedule vaccination (D194)
	T cell response	Before the first dose of inoculation (D0), 14 days after the first dose of inoculation (D14), 14 days after the whole schedule vaccination (D28)
Phase I - routine immunization schedule	Neutralizing antibody, IgG, IgM	Before the first dose of inoculation (D0), 28 days after the first dose of inoculation (D28), 35 days after the first dose of inoculation (D35), 42 days after the first dose of inoculation (D42), 56 days after the first dose of inoculation (D56), 6 months after the whole schedule vaccination (D208)
	T cell response	Before the first dose of inoculation (D0), 28 days after the first dose of inoculation (D28), 42 days after the first dose of inoculation (D42)
Phase II - emergency immunization schedule	Neutralizing antibody	Before the first dose of inoculation (D0), 14 days after the whole schedule vaccination (D28), 42 days after the first dose of inoculation (D42), 6 months after the whole schedule vaccination (D194)
Phase II - routine immunization schedule	Neutralizing antibody	Before the first dose of inoculation (D0), 28 days after the whole schedule vaccination (D56), 6 months after the whole schedule vaccination (D208)

This study was carried out by the Jiangsu Provincial Center for Disease Control and Prevention (Public Health Research Institute of Jiangsu Province).

## 3.2 Randomization and Double Blinding

### 3.2.1 Randomization

In phase I and phase II clinical trial, the blinding code of emergency and routine immunization schedule should be generated separately by the randomization statistician by the method of block randomization using SAS software (version 9.4). The blinding code refers to the list of the correspondence between the random number and the trial products (i.e., vaccine or placebo), which is prepared in duplicate and should be sealed after the completion of the blind coding. The original copy should be kept by the investigator for unblinding of the trial, and the duplicate copy should be kept by the sponsor. In the phase I clinical trial, the vaccine (or placebo) numbers for the emergency immunization schedule and that for the routine immunization schedule are A001-A072 and B001-B072 respectively. In the phase II clinical trial, the vaccine (or placebo) number numbers for the emergency immunization schedule and that for the routine immunization schedule are C001-C300 and D001 and D300.

The blinding code of the backup vaccine (or placebo) is also generated by the randomization statistician using SAS software (version 9.4). In the phase I clinical trial, the backup vaccine (or placebo) is prepared in a 1:1:1 ratio of medium dosage, high dosage vaccine, and placebo, and the backup vaccine (or placebo) numbers are X01-X036. In phase II clinical trial, the backup vaccine (or placebo) is prepared in a 2:2:1 ratio of medium dosage, high dosage vaccine, and placebo. In case of the circumstances such as color change and damage of the trial products, the inoculation personnel should report to the person in charge of the site and principle investigator, the initiation schedule of the backup vaccine should be started up, a backup vaccine (or placebo) number should be obtained through the online backup vaccine acquisition system, and the corresponding backup vaccine should be used instead of the problem vaccine.

### 3.2.2 Double Blinding

In this study, a double-blind design is adopted, in which the randomization statistician and other personnel who do not participate in the trial will engaged in vaccine (or placebo) blinding, i.e. pasting the printed number label to the specified location of the vaccine (or placebo), according to the generated blinding code. The whole process of vaccine (or placebo) blinding will be supervised by the randomization statistician. The blinding code should be sealed after the completion of the blind coding. The whole process of blinding must be recorded in writing. Personnel who conduct blinding are forbidden to participate in other relevant work of this clinical trial, and should not disclose the blinding code to any person participating in this clinical trial.

### 3.3 Sample Size

**Clinical trial phase I:** According to the requirements of the *Good Clinical Practice* and *Provisions for Drug Registration*, phase I clinical trial is a small size study aims to safety evaluation. The total sample size of phase I are 144 subjects, with a total of 72 subjects for each immunization schedule, and 48 subjects receive medium or high dosage investigational vaccine for each immunization schedule. The sample size meets the requirements of the phase I clinical trial.

**Clinical trial phase II:** According to the requirements of the *Good Clinical Practice* and *Provisions for Drug Registration*, the phase II clinical trial mainly evaluates the immunogenicity and safety of different dosage vaccine in the targeted subjects and the sample size is more than 300. The total number of subjects in phase II is 600, with that of subjects receive medium, high dosage vaccine and placebo as 240, 240, and 120 respectively. Thus, the subjects in the trial group are 480. The sample size meets the requirement of phase II clinical trial.

## 4. Clinical Trial Endpoint

### 4.1 Endpoint of Phase I

#### 4.1.1 Immunogenicity Endpoint

The immunogenicity endpoints were defined on the 7th, 14th, 21st, 28th, 42nd days after the first dose of the emergency immunization schedule and the 28th, 35th, 42nd, 56th day after the first dose of the routine immunization schedule:

- (1) Post-immunization neutralization antibody  $\geq 4$  rate: post-immunization neutralization antibody titer  $\geq 1:4$
- (2) Post-immunization neutralizing antibody titer  $\geq 4$  in the subjects with pre-immunization  $< 4$ : those whose neutralizing antibody titer was less than 1:4 before immunization, and the neutralizing antibody titer  $\geq 1:4$  after immunization
- (3) The 4-time increase rate of neutralizing antibody after immunization in the subjects  $\geq 4$  before immunization: the subjects with  $\geq 4$  before immunization was defined as those with neutralizing antibody titer  $\geq 1:4$  before immunization, and those with neutralizing antibody titer increased by 4 times or more after immunization
- (4) Post-immunization seroconversion rate-1: pre-immunization neutralizing antibody titer  $< 1:4$  and post-immunization neutralizing antibody titer  $\geq 1:4$ ; or pre-immunization neutralizing antibody titer  $\geq 1:4$ , post-immunization neutralizing antibody titer increased by 4 times or more than that before immunization
- (5) Post-immunization neutralization antibody  $\geq 8$  rate: post-immunization neutralization antibody titer  $\geq 1:8$
- (6) Post-immunization neutralizing antibody titer  $\geq 8$  in the subjects with pre-immunization  $< 8$ : those whose neutralizing antibody titer was less than 1:8 before immunization, and the neutralizing antibody titer  $\geq 1:8$  after immunization
- (7) The 4-time increase rate of neutralizing antibody after immunization in the subjects  $\geq 8$  before immunization: the subjects with  $\geq 8$  before immunization was defined as those with neutralizing antibody titer  $\geq 1:8$  before immunization, and those with neutralizing antibody titer increased by 4 times or more after immunization
- (8) Post-immunization seroconversion rate-2: pre-immunization neutralizing antibody titer  $< 1:8$  and post-immunization neutralizing antibody titer  $\geq 1:8$ ; or pre-immunization neutralizing antibody titer  $\geq 1:8$ , post-immunization neutralizing antibody titer increased by 4 times or more than that before immunization
- (9) Post-immunization neutralizing antibody GMT and GMI
- (10) Post-immunization neutralizing antibody GMT and GMI in the subjects with pre-immunization  $< 4$
- (11) Post-immunization neutralizing antibody GMT and GMI in the subjects with post-immunization  $\geq 4$
- (12) Post-immunization neutralizing antibody GMT and GMI in the subjects with pre-immunization  $< 8$

- (13) Post-immunization neutralizing antibody GMT and GMI in the subjects with post-immunization  $\geq 8$
- (14) Post-immunization positive rate of antibody IgG: the S/CO value of antibody IgG after immunization  $\geq 1$
- (15) Post-immunization positive rate of antibody IgM: the S/CO value of antibody IgM after immunization  $\geq 1$

#### 4.1.2 Exploratory Endpoint

The following exploratory endpoints were defined for emergency and routine immunization schedules, respectively:

- (1) Neutralization antibody  $\geq 4$  rate at 6 months after the whole schedule vaccination
- (2) Neutralization antibody  $\geq 8$  rate at 6 months after the whole schedule vaccination
- (3) GMT of neutralizing antibody at 6 months after the whole schedule vaccination
- (4) The positive rate of T cell response assay (IFN- $\gamma$  detection) at 14 days after the first dose of inoculation (emergency immunization schedule) or 28 days after the first dose of inoculation (routine immunization schedule)
- (5) The positive rate of T cell response assay (IFN- $\gamma$  detection) at 14 days after the whole schedule vaccination

IFN- $\gamma$  positive was defined as the average number of negative control  $< 6$ , the average number of peptide stimulation wells - negative control  $> 6$ ; or when the average number of negative control was  $\geq 6$ , the average number of peptide stimulation wells / negative control points was  $\geq 2$ .

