## 6.5 Exploratory Analysis

(1) The statistical method for exploratory evaluation for emergency immunization schedule and routine immunization schedule in Phase I is summarised as follows.

The following rates will be calculated by the group and their confidence intervals will be estimated by the Clopper-Pearson method:

- Rate of serum neutralizing antibody titer no less than 4 at 6 months after the whole schedule vaccination,
- Rate of serum neutralizing antibody titer no less than 8 at 6 months after the whole schedule vaccination,
- Positive rate of T cell response (IFN- $\gamma$  detection using Elispot) at 14/28 days after the first dose in emergency immunization schedule/ routine immunization schedule,
- Positive rate of T cell response (IFN- $\gamma$  detection using Elispot) at 14 days after the whole schedule vaccination,

Chi-square test or Fisher exact test will be used to detect differences among groups per rate as above. Furthermore, if statistically significant, pairwise comparison will be conducted between groups by Chi-square test or Fisher exact test. Additionally, using the same method, their comparison between emergency immunization schedule and routine immunization schedule will be conducted by group (medium-dose group and high-dose group), respectively.

Descriptive statistics for the difference between the average number of stimulation holes for T cell response assay (IFN- $\gamma$  detection using Elispot method) and that of negative control on day 14 (emergency immunization schedule) / 28 (routine immunization schedule) after the first dose of immunization will be provided by group. Rank-sum test will be used to test the difference among groups. Furthermore, if statistically significance exists, pairwise comparison will be conducted between groups by rank-sum test.

Descriptive statistics for GMT at 6 months after the whole schedule vaccination, including geometric mean and 95% confidence interval (95% CI), will be provided by the group. Furthermore, if statistically significance exists, group t-test with log-transformation will be conducted between groups. Additionally, using the same method, T cell response assay (IFN- $\gamma$  detection using Elispot method) comparison between emergency immunization schedule and routine immunization schedule will be conducted by group (medium-dose group and high-dose group), respectively.

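### The D0 ELISpot sample has no stated use in the SAP, so Phase I T-cell positive rates cannot separate pre-existing from new reactivity

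*SAP*

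**What the plan says.** **Sampling.** In SAP section 3.1, Table 2 lists the T-cell samples for Phase I. The emergency schedule has "Before the first dose of inoculation (D0), 14 days after the first dose of inoculation (D14), 14 days after the whole schedule vaccination (D28"). The routine schedule has "Before the first dose of inoculation (D0), 28 days after the first dose of inoculation (D28), 42 days after the first dose of inoculation (D42"). Each schedule thus has one baseline and two post-dose samples.

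**Endpoints and positivity rule.** Section 4.1.2 defines two T-cell positive rates. One is taken "at 14 days after the first dose of inoculation (emergency immunization schedule) or 28 days after the first dose of inoculation (routine immunization schedule"), the other 14 days after the full schedule. The rule has two branches, depending on whether the negative control averages below 6. It begins "positive was defined as the average number of negative control". The first branch needs peptide wells minus control to exceed 6. In the second, "the average number of peptide stimulation wells / negative control points was" at least 2. Neither branch contains a D0 value.

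**Analysis.** For the positive rates, section 6.5 states: "Chi-square test or Fisher exact test will be used to detect differences among groups per rate as above". It then plans "Descriptive statistics for the difference between the average number of stimulation holes for T cell response assay" and the negative control at the first post-dose visit, with rank-sum tests. It also compares the emergency with the routine schedule within the medium-dose and high-dose groups. Change from D0, a D0-negative subset and a D0 covariate are all absent.

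**Baseline.** Section 6.3 lists IgG and IgM at baseline but not ELISpot.

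**The concern.** The negative-control well removes background spots in that day's assay. It does not show whether the subject already reacted to the peptides before the first dose. Only the D0 sample can show that, and the SAP gives it no role. A subject who is reactive at D0 and stays so is counted as positive after vaccination in the same way as a new responder.

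The SAP treats other measures differently. Neutralizing antibody has seroconversion, GMI and subsets by pre-immunization titer (4.1.1). Laboratory parameters have change from baseline and shift tables (6.6.2).

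Two outputs are at stake:
- **The per-group rates and their Clopper-Pearson intervals**, which a reader may take as responses to vaccine.
- **The schedule comparison by dose group**, which uses no placebo group. Section 3.2.1 generates the codes for the two schedules separately, and section 3.1 does not describe randomization between schedules. Any D0 difference between schedules would pass straight into that comparison.

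**Working it through.** The plan states no figure that depends on this point, so there is none to reproduce. The group sizes do check: 36 × 2/3 = 24 vaccine and 12 placebo per dosage stage, and 72 × 2/3 = 48 vaccine recipients per schedule, as section 3.3 says.

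**Assumptions, since the SAP gives neither quantity.** Let b be the proportion reactive at D0 and v the new response among D0-negative vaccine recipients. Take v = 30%. Placebo is taken as 12 + 12 = 24 pooled within a schedule. D0 reactivity is assumed to persist, and new placebo positives are assumed to be zero.

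- Reported vaccine-group rate = b + (1 − b)v. For b = 10%: 0.10 + 0.90 × 0.30 = 37%.
- Share of vaccine-group positives already reactive at D0 = b / [b + (1 − b)v]. For b = 10%: 0.10/0.37 = 27%.
- Vaccine minus placebo = (1 − b)v. For b = 10%: 0.90 × 0.30 = 27 points.
- Power is exact two-sided Fisher at 0.05. The D0-negative column uses about 24(1 − b) per arm.

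| b | Reported vaccine rate | Already reactive at D0 | Vaccine minus placebo | Power, current rule (24 v 24) | Power among D0-negatives (n per arm) |
|---|---|---|---|---|---|
| 0% | 30% | 0% | 30 points | 0.89 | 0.89 (24) |
| 5% | 33.5% | 15% | 28.5 points | 0.67 | 0.86 (23) |
| 10% | 37% | 27% | 27 points | 0.52 | 0.84 (22) |
| 20% | 44% | 45% | 24 points | 0.33 | 0.72 (19) |
| 30% | 51% | 59% | 21 points | 0.24 | 0.61 (17) |

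As b rises, the per-group rate goes up while the vaccine-placebo difference shrinks.

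**New positives on placebo.** With 2% new positives among D0-negative placebo subjects, power among D0-negatives is 0.69 (b = 10%) and 0.58 (b = 20%). Under the current rule with the same 2%, the placebo rates are 0.10 + 0.90 × 0.02 = 11.8% and 0.20 + 0.80 × 0.02 = 21.6%, and power is 0.44 and 0.28.

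**If D0 positivity is assay noise.** Suppose positivity at D0 is independent of later visits. Dropping D0-positive subjects then removes people but not background. The comparison becomes 37% v 10% at 22 per arm (0.463, against 0.52 at 24) or 44% v 20% at 19 per arm (0.255, against 0.33). Under this assumption the restriction loses power.

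**Schedule comparison.** With the same v = 30% in both schedules but b = 10% in one and 20% in the other, the reported rates are 37% and 44%, a 7-point gap due to baseline alone. Chance is enough to produce unequal baselines: two groups of 24 with the same b differ by three or more D0-positive subjects with probability 22% at b = 10% and 36% at b = 20%.

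**The case against.** The strongest reply is that the endpoint is a positive rate at a visit. Section 4.1.2 does not call it an induced rate. Post-dose positivity alone is also used for IgG, IgM and the ≥4 and ≥8 antibody rates. The rule can be computed as written and conflicts with nothing else in the document. This stands.

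A reader might go further and infer that the plan credits pre-existing reactivity to the vaccine and so exaggerates its effect over placebo. The document does not support that. Section 3.1 randomizes 2:1 within each dosage stage, so placebo subjects carry the same expected D0 reactivity. The difference is diluted, not inflated.

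A reader might also take the power gain from restricting to D0-negative subjects as established. It is not: it depends on D0 positivity persisting, and it reverses if that positivity is independent noise. The SAP supports neither assumption over the other.

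Two simple remedies have defects of their own. A responder rule limited to D0-negative subjects cannot count a boosted response in a D0-positive subject, whereas the SAP's seroconversion definition does count a rise from a positive baseline. A raw change score can be noisier than the post-dose value when within-subject correlation is low.

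Finally, section 7 puts the analysis tables in a separate appendix that is not at hand. It may contain a D0 summary. The SAP text still assigns D0 no rule or analysis.

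None of this answers the points about the per-group rates or the schedule comparison.

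**Conclusion.** The point holds as a gap in the analysis text: a planned baseline sample is left without a stated use. It limits what the per-group T-cell rates can mean and leaves the emergency-versus-routine comparison without control for D0 differences. For vaccine against placebo, the cost is dilution and lost precision, and only if D0 reactivity exists and persists.

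The size cannot be fixed from the document. For assumed D0 reactivity of 5% to 30% and a 30% new response, the reported vaccine-group rate is 33.5% to 51%. With no D0-positive subject the effect is nil. Only the D0 data can show which case applies, and the text does not plan to summarize them.

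Severity is modest. The endpoint is exploratory and Phase I only, and section 6.7 makes all p-values nominal.

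**What to change.** Amend sections 6.3 and 6.5 before unblinding, so that the rule is not chosen after seeing results:

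1. Tabulate D0 ELISpot positivity and background-subtracted counts by group and schedule.
2. Keep the current visit-level positive rate. Beside it, report the rate of new positivity among D0-negative subjects, and show D0-positive subjects separately so that boosted responses are not lost.
3. Compare post-dose background-subtracted counts with adjustment for the D0 value, for example by rank-based ANCOVA, rather than by a raw change score. Do the same for the schedule comparison within dose groups.

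The cost is SAP wording and a few derived variables; the samples are already planned. The downsides are a slightly smaller denominator for the new-positive rate and a possible small loss of power if D0 positivity is mainly assay noise.
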